2.2. SECONDARY OBJECTIVES

To measure the impact that pregnancy symptoms and treatments have on women's lives.

Examples of the overarching questions and measures include:

- Nausea and vomiting during pregnancy – to identify how often this affects pregnancy, its timing, treatments, and impact on weight
 - How often and at what gestational age do nausea and vomiting begin/improve?
 - Impact on weight
 - Treatments
- Physical disabilities and pregnancy – to identify how many pregnancies may be affected by physical disabilities
 - What disability?
 - Impact on pregnancy
 - Impact of pregnancy on the condition
- Weight gain in pregnancy – to identify weight gain patterns in pregnancy and compare to Institute of Medicine guidelines
 - Pre-pregnancy weight and height
 - Weight weekly or monthly
 - Plot weight gain on the appropriate IOM guideline chart
- Activity/Exercise in pregnancy – to identify exercise patterns in pregnancy including type and amount of exercise, impact on pregnancy
 - Evaluation of moderate and high impact activities across pregnancy
- Sleep in pregnancy – to identify sleep patterns in pregnancy including number of hours, sleep quality, and sleep position
 - Sleep pattern prior to pregnancy
 - Number of hours (on average) sleep per night
 - Quality of sleep
 - Prevalence of sleep apnea
 - Sleep position
- Mood in Pregnancy – to identify general mood in pregnant women throughout gestation. This will be done via a Mood Tracker and mood may be entered as often as necessary. We will use the validated Positive and Negative Affect Schedule (PANAS)

(Watson D and Clark LA 1994; Thompson ER 2007). This measure has also been used to access psychological stress among women with and without reproductive failure (Coughlan C et al 2014). It may collect mood descriptions such as excited, irritable, angry, jittery, etc.

- Medications in pregnancy – to identify how many medications women are taking, reasons for their use, and how many are taken without clinician recommendation
 - Any medications used (weekly query) with triggers of those input in prior week to allow a continuation or stopping of that medication
 - Reason for the medication being used
 - Did a medical provider recommend the medication or is it being used over the counter?

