2.3.2. Secondary Outcome Measures

- Proportion of pregnant women who experience nausea and vomiting in pregnancy across gestation
- Proportion of pregnancies that are impacted by physical disabilities
- Weight gain patterns in pregnancy with a comparison to IOM guidelines
- Exercise patterns in pregnancy including type and amount of exercise, impact on pregnancy
- Sleep patterns in pregnancy including number of hours, sleep quality, and sleep position
- How many medications women are taking, reasons for their use, and how many are taken without clinician recommendation
- How many alternative medications /herbal supplements pregnant women are taking, reasons for their use, and how many are taken without clinician recommendation
- Number of ultrasounds in pregnancy

In the future, additional measures may be added, such as assessments of maternal mental health, stress, chronic conditions such as hypertension and diabetes, and assessment of maternal diet and other environmental factors.

SECTION 3. STUDY POPULATION

This will be a prospective cohort study, collecting information from women of child-bearing age who are pregnant. The study will include healthy volunteers, as well as those with pre-conception medical conditions and/or pregnancy complications. Because it will be online, there is no limit to the number of participants who can join. It will be focused on women in the United States, but because it will be online, women in other countries may also participate.

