- Number of hours of sleep each night
- Quality of sleep (slept soundly, tossed and turned, etc.)
- Sleep position (back, stomach, right side, left side)

Activity tracker. Activity could be entered as often as necessary. It may collect data on:

- Intensity of physical activity
- Duration of physical activity

Mood tracker. The Mood Tracker could be entered as often as necessary. We will use the validated Positive and Negative Affect Schedule (PANAS) (Watson D and Clark LA 1994; Thompson ER 2007). This measure has also been used to access psychological stress among women with and without reproductive failure (Coughlan C et al 2014). It may collect:

- Mood description

As per Section 7.1.1.1 Safety: "If a participant enters data indicating a health or safety concern, the database will send an automated notice to her that she may want to contact her doctor for advice. The database may also refer her to related factsheets and websites with further information." In PregSourceSM, after a participant enters data for the PANAS, the platform will calculate raw scores for both positive affect (PA) and negative affect (NA). Crawford (2010) reported norms for the PA and NA scores on the PANAS instrument. Because the data were not normally distributed, they converted the data into percentiles. The Crawford nomogram will be used to convert raw scores into percentiles. Participants who score >95th percentile for NA and/or <5th percentile for PA will be considered to have affect that deserves further attention by a clinician. Participants with scores in these ranges will receive a notification stating that their mood may indicate a problem that they may want to discuss with their care provider. Participants will also receive a follow-up message 2 weeks after the initial notification

⁷ Height data would be collected in the Initial Health Questionnaire, so that BMI can be calculated. We would ask in the Gestational Age monthly questionnaires if there was any change in height (not likely for adults, but may change for teenagers).

reminding them that their mood tracker indicated a concern that may warrant discussion with their health care provider.

Medications in pregnancy tracker. The Medications Tracker may ask if the women have:

- Taken any medications for specific conditions
- When they stopped taking the medication
- Reason for the medication being used

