Alternative therapies tracker. The Alternative Therapies Tracker may ask women if they are taking any alternative medications or herbal supplements, reasons for their use, and how many are taken without clinician recommendation:

- Any herbal supplements or alternative medications used?
- If yes, which therapies?
- Reason for use

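### Minor: the example medication question in section 2.2 sets provider recommendation against over-the-counter use, so as worded it cannot reliably count medications taken without a clinician's recommendation

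*Protocol*

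**What the plan says.** The medications entry in Protocol section 2.2 gives its aim as "to identify how many medications women are taking, reasons for their use, and how many are taken without clinician recommendation". Section 2.3.2 repeats this among the secondary outcome measures: "How many medications women are taking, reasons for their use, and how many are taken without clinician recommendation".

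Under the aim, section 2.2 lists three lines: a weekly query on use, the reason for use, and "Did a medical provider recommend the medication or is it being used over the counter". The weekly query comes "with triggers of those input in prior week to allow a continuation or stopping of that medication". The whole list is introduced by "Examples of the overarching questions and measures include".

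Section 4.4.2.1 describes the Medications Tracker tentatively: "The Medications Tracker may ask if the women have". Three items follow: "Taken any medications for specific conditions", the time of stopping, and the reason for use. The lead-in to the Alternative Therapies Tracker in the same section says it may ask about "alternative medications or herbal supplements, reasons for their use, and how many are taken without clinician recommendation".

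**The concern.** The outcome depends on one attribute of each product: whether a clinician recommended it. The example question instead asks the woman to choose between that attribute and another, whether the product is used over the counter. The two are not opposites. A clinician may recommend a product sold over the counter, and a woman may take a medicine that is not over the counter without anyone recommending it to her, for example one left over from an earlier prescription.

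If the line became the questionnaire item unchanged, recommendation status would not be recorded on its own, and the count of unrecommended medications would mix the two attributes. Rewording the question after launch would leave use already reported to be corrected from recall. The number of medications and the reasons for use are not affected.

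**Working it through.** The protocol attaches no figure to this outcome, so there is nothing to reproduce. The check cross-classifies products by the two attributes and compares what the question records with what the outcome needs.

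**Inputs.** The target comes from sections 2.2 and 2.3.2, and the question from section 2.2. The shares below are symbols, because the protocol gives no values for them.

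**Step 1: fitting answers by product type.** Let a, b, c and d be shares of all medications reported, with a + b + c + d = 1.

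| Type | Recommended | Over the counter | Fitting answers |
|---|---|---|---|
| a | yes | no | 1 (recommended) |
| b | yes | yes | 2 (both) |
| c | no | yes | 1 (over the counter) |
| d | no | no | 0 (neither) |

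Exactly one answer fits in 2 of the 4 types.

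**Step 2: target and recorded value.** The true unrecommended share is c + d. Suppose each over-the-counter answer is counted as unrecommended, and types a and c give their single fitting answer. Let f be the share of type b, and g the share of type d, answered as over the counter. Then:

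- recorded share = c + f·b + g·d
- error = (c + f·b + g·d) − (c + d) = f·b − (1 − g)·d

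**Step 3: bounds.** With f = 0 and g = 0 the error is −d, because all unrecommended products that are not over the counter are missed. With f = 1 and g = 1 it is +b, because all recommended over-the-counter products are counted as unrecommended. The error lies between −d and +b, and its sign is not fixed. Since b, d, f and g are all unknown, no percentage follows.

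**Step 4: what product names could recover.** If names are captured, they could show whether a product is prescription or over the counter. Among over-the-counter products, those answered as over the counter make up c + f·b. The name does not separate c from f·b, because it says nothing about whether a clinician recommended the product. The repair is partial.

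**The case against.** The strongest reply is that the line may not be questionnaire text at all. It stands in a list of examples, beside entries on treatments, on plotting weight against a guideline chart and on sleep apnea prevalence, which are topics rather than questions to put to a participant. The final questionnaires are not in the document. This stands, and it makes the point conditional on the line being used as worded. It does not remove the point: the line is phrased as a question, and it is the only wording the protocol offers for this part of the medication outcome.

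A reader might also infer that the Medications Tracker omits recommendation status, since none of its three listed items mentions it. The text does not support that as a separate error. The tracker list says only what may be asked. The Alternative Therapies Tracker names use without recommendation in its lead-in and then leaves it out of its own bullets, so these lists are plainly not complete. The silence is missing detail.

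There are also existing chances to catch the wording. Beta testers are to answer questions about the surveys and trackers before launch (section 4.4.6), and the investigators intend to keep revising questions (section 4.4.2.4). Both count in the protocol's favour, though neither is directed at this question.

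Finally, the registry is descriptive and has no pre-planned statistical analysis (section 8.1). That lowers the importance of the point. It does not help with an attribute that was never recorded separately.

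**Conclusion.** The point holds as a minor, conditional one. If the example question is used as worded, it cannot reliably give the number of medications taken without a clinician's recommendation, because two of the four product types have no single fitting answer. The error, as a share of medications reported, lies between minus the share that is unrecommended and not over the counter, and plus the share that is recommended and over the counter. The protocol gives neither share, nor how women would answer in those cases, so size and direction stay open.

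The conclusion assumes that over-the-counter answers would be counted as unrecommended and that women with an unambiguous product answer correctly. It reaches one component of one descriptive secondary outcome. A reader might go further and conclude that the outcome is certain to be lost or that no later step could help. The text does not support this: the final wording is not fixed, and product names could settle prescription or over-the-counter status, though not recommendation.

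**What to change.** Before launch, replace the line in section 2.2 with two questions per product, asked once when the product is first entered:

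1. Is it a prescription or an over-the-counter product?
2. Did a health care provider recommend or prescribe it? (yes / no / unsure)

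Derive the unrecommended count from question 2 only, and report the unsure answers as their own category. Add question 2 to the Medications Tracker list in section 4.4.2.1 so that it matches section 2.2. Asking once should be enough, because the weekly query already brings back the products entered the week before.

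The cost is one or two extra response fields per product, matching wording in two sections, and slightly more burden for participants.

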2.3. OUTCOME MEASURES

PregSourceSM is a research registry for gathering longitudinal, observational data from women during their pregnancies. It, therefore, does not have specific outcome measures beyond descriptive data on women’s experiences and pregnancy outcomes.

It will provide the following benefits:

- Allow participants to compare their personal health situation to the summarized, de-identified information from other participants, and links to evidence-based information sources
- Provide de-identified data to approved researchers for analysis on etiology, natural history, and/or treatment effectiveness on issues related to pregnancy
- Identify pregnant women who may be eligible and interested in participating in clinical studies and trials

Below is a sample of outcome measures that PregSourceSM will collect and analyze.

2.3.1. Primary Outcome Measures

- Gestational age of delivery
- Birthweight of baby
- Maternal gestational weight gain
- Health of baby and mom

2.3.2. Secondary Outcome Measures

- Proportion of pregnant women who experience nausea and vomiting in pregnancy across gestation
- Proportion of pregnancies that are impacted by physical disabilities
- Weight gain patterns in pregnancy with a comparison to IOM guidelines
- Exercise patterns in pregnancy including type and amount of exercise, impact on pregnancy
- Sleep patterns in pregnancy including number of hours, sleep quality, and sleep position
- How many medications women are taking, reasons for their use, and how many are taken without clinician recommendation
- How many alternative medications /herbal supplements pregnant women are taking, reasons for their use, and how many are taken without clinician recommendation
- Number of ultrasounds in pregnancy

In the future, additional measures may be added, such as assessments of maternal mental health, stress, chronic conditions such as hypertension and diabetes, and assessment of maternal diet and other environmental factors.

SECTION 3. STUDY POPULATION

This will be a prospective cohort study, collecting information from women of child-bearing age who are pregnant. The study will include healthy volunteers, as well as those with pre-conception medical conditions and/or pregnancy complications. Because it will be online, there is no limit to the number of participants who can join. It will be focused on women in the United States, but because it will be online, women in other countries may also participate.

3.1. INCLUSION CRITERIA

- Women who are pregnant and over 18 and under 70 years of age.

3.2. EXCLUSION CRITERIA

- Males
- Women who are not pregnant
- Minors under age 18
- Women over the age of 70
- Women who are unable to provide consent for themselves

SECTION 4. STUDY DESIGN AND METHODS

4.1. STUDY OVERVIEW

PregSourceSM is a participant opt-in research registry. A pregnant woman can go online to the Website or download the app to join directly at a time of her choosing. PregSourceSM will not provide medical advice, treatments, or evaluations, for either clinical or research purposes, and the participant will not be required to visit a doctor, complete any medical examinations, or provide biological samples in order to participate.

Registry questions cover the time period from pre-conception through pregnancy and the post-partum period until 36 months, including neonatal outcomes. A participant can remain in the study as long as she chooses. It is possible, but not required, that she could remain in the study between pregnancies, entering information for multiple pregnancies.

PregSourceSM will be run on a web-based platform under contract with Lockheed Martin Management Systems Designers, Inc. and its affiliated subcontractor, PatientCrossroads, Inc. (collectively referred to as “Contractor”). The platform will capture participant information using condition-specific elements, as well as existing Common Data Elements (<http://www.nlm.nih.gov/cde/>).

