4.4.2. Account Profile Set up and Health History Questionnaire

Once registered and consented, a participant can begin to enter information after reading the PregSourceSM Privacy Policy and Terms and Conditions of use, then completing her Account Profile and taking an initial Health History questionnaire to collect data on:

- Contact information and preferences (email, text, etc.), including an optional alternate contact²
- Demographics and socioeconomic -- NIH-required race/ethnicity data, general family income ranges, education levels

² Alternate Contacts will be contacted only in cases when repeated attempts to gather final pregnancy outcome information have been unsuccessful.

- Interest in participating in a clinical trial. The participant will be asked for her consent to allow the PregSourceSM coordinators to contact her regarding future opportunities for participation in a clinical trial or research study.
- Pre-pregnancy general health – height, weight, a checklist for chronic conditions (e.g., diabetes, lupus), medications
- Reproductive health – contraceptive use, previous pregnancy histories, infertility, use of assisted reproductive technologies
- Current pregnancy health – gestational age, number of fetuses, date of first prenatal visit, prenatal visits completed, any diagnoses received or test results.

A participant will access PregSourceSM questionnaires online and/or via a mobile app to enter her own data. She will be able to download apps (e.g., via the iTunes or Android online app stores) to a smartphone or tablet, and connect these to her online account.³ The apps, as well as the Website, will let her access and enter data into online surveys and trackers. A participant will also be sent reminders and push notifications, asking her to update her information.

All questionnaires will be constructed using “Smart Survey Design” – i.e., using conditional or skip logic to add or skip questions that are not relevant, based on previous answers. Aggregated data will help us analyze response frequencies for survey questions.

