4.4.2.1. Trackers

Each participant can enter data in a set of health “trackers” – online or in-app software diaries that capture daily or weekly information over the course of pregnancy about her weight, nausea symptoms, mood, and sleep. Additional trackers may be added at a later date for tracking nutrition, exercise, and pain. She can enter data in the trackers as often as she chooses. We anticipate that for trackers such as nausea, sleep, and mood, a participant might enter data on a daily basis; while weight data might be entered only once a week or even once a month. Most trackers will collect data on timing, duration, severity/intensity, and related issues. A 2013 report by Citrix⁴, a software company that tracks app usage, shows pregnancy related apps to have wider usage. Many of the available trackers have been used and/or validated in the pregnant population⁵. Recent research articles⁶ have demonstrated the use of web-based methods to collect relevant health related information from pregnant women.

Unless otherwise indicated in her Account Profile, a participant will be reminded on a weekly basis to update her information, if she has not entered new data within the past two weeks.

³ Participants will not be required to use the apps. The apps will be available as a potentially more readily available means of accessing the questionnaires and trackers.

⁴ Nick Bilton, New York Times, August 26, 2015

⁵ Hämeen-Anttila K, Nordeng H, Kokki E, Jyrkkä J, Lupattelli A, Vainio K, Enlund H. Multiple information sources and consequences of conflicting information about medicine use during pregnancy: a multinational Internet-based survey. *J Med Internet Res.* 2014 Feb 20;16(2).

⁶ Wise LA, Mikkelsen EM, Rothman KJ, Riis AH, Sørensen HT, Huybrechts KF, Hatch EE. A prospective cohort study of menstrual characteristics and time to pregnancy. *Am J Epidemiol.* 2011 Sep 15;174(6):701-9

We anticipate including the following trackers:

Weight tracker. Weight would likely be entered weekly/monthly. Data collected includes:

- Weight (in pounds or kilograms)⁷

Nausea tracker. The Nausea Tracker could be entered as often as necessary, collecting data on:

- Date
- Timing (morning, afternoon, all day)
- Duration
- Severity (just nauseous, vomited)

Sleep tracker. In addition to asking about a participant's sleep patterns and apnea diagnosis prior to pregnancy in the initial health questionnaire, the Sleep Tracker may collect data on:

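### Entry is open at any gestational age, but the protocol lists no look-back on nausea earlier in the pregnancy, so onset and ever-frequency cannot be recovered for women who join late

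*Protocol*

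**What the plan says.** **Entry.** Section 4.1 lets a woman "join directly at a time of her choosing". The only inclusion criterion in 3.1 is "Women who are pregnant and over 18 and under 70 years of age", with no gestational window. Section 7.2.3 itself expects women to enrol at differing gestational ages.

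**Aims.** The first question in Section 1 concerns how many women have morning sickness, how long it lasts and when in gestation it occurs. Section 2.2 asks "How often and at what gestational age do nausea and vomiting begin/improve". Section 2.3.2 lists as a secondary outcome "Proportion of pregnant women who experience nausea and vomiting in pregnancy across gestation".

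**Capture at enrolment.** For the current pregnancy, the Health History content in 4.4.2 is "gestational age, number of fetuses, date of first prenatal visit, prenatal visits completed, any diagnoses received or test results". No symptom history is listed.

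**Capture afterwards.** Section 4.4.2.1 says "The Nausea Tracker could be entered as often as necessary, collecting data on" date, time of day, duration and severity. Use is at the woman's discretion. The monthly questionnaires (4.4.2.2) are matched to the current week of gestation. A woman who has not used the trackers in the past month is sent to them, so that questions are not duplicated.

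**Look-back elsewhere.** The sleep tracker comes "In addition to asking about a participant's sleep patterns and apnea diagnosis prior to pregnancy in the initial health questionnaire". Section 2.2 also asks when in gestation herbal supplements were used and for how long.

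**Analysis.** Section 8.1 states that none is pre-planned.

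**The concern.** Nausea is largely a feature of early pregnancy, while entry is open throughout. A woman who joins after her nausea began has an onset that lies before her first possible contemporaneous record. A woman whose nausea has already stopped may leave no record of it at all. If nobody asks her, no later analysis can supply the missing fact. Gestational age at entry shows which women joined late, but not whether or when they were nauseated.

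This is a matter of what is collected, so a statistical analysis plan could not repair it. At stake are the 2.2 question on when nausea begins and the Section 1 questions on how many and how long. The answers would depend on when women happen to enrol. They would also reach participants directly, because 6.4.2 promises a woman with morning sickness a view of how many others in the database report it.

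**Working it through.** **1. Is there a figure to reproduce?** No. The protocol gives no nausea rate, no onset distribution and no distribution of gestational age at entry. Everything numerical below is illustrative.

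**2. Can any described route recover pre-entry nausea?**

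- Enrolment (4.4.2): gestational age, fetuses, visits, diagnoses and tests. Diagnoses would catch only nausea that received a diagnosis.
- Tracker (4.4.2.1): has a date field, but describes no onset item and no prompt for past episodes.
- Monthly questionnaire (4.4.2.2): tied to the current week; no nausea look-back is described.

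No route is named.

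**3. Illustration.** Assumptions: 70% truly affected; onset normal with mean week 6, SD 1.5 (not before week 3); end normal with mean week 14, SD 4 (at least one week after onset); entry uniform from week 4 to week U and unrelated to nausea; only nausea present after entry is recorded. There were 1,000,000 simulated women per scenario.

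- Ever-nausea recorded among all enrolees = 0.70 × P(end > entry).
- First recorded nausea = the later of onset and entry.
- Share of affected women who enrol before onset = E[(onset − 4)⁺] / (U − 4), where E[(onset − 4)⁺] = 2 × Φ(1.333) + 1.5 × φ(1.333) = 2.06.

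| Entry weeks | Ever-nausea recorded (true 70%) | Mean first recorded week (true 6.0) | Affected women enrolled before onset |
|---|---|---|---|
| 4–12 | 64% | 8.2 | 2.06/8 = 26% |
| 4–20 | 44% | 9.9 | 2.06/16 = 13% |
| 4–40 | 20% | 10.1 | 2.06/36 = 6% |

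Hand check of the last row: the mean end is 14.1 weeks after the truncation, so 0.70 × (14.1 − 4)/36 = 0.196.

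**4. Sensitivity to the assumed truth.** For entry over weeks 4–12, 4–20 and 4–40, a true 50% is recorded as 46%, 31% and 14%. A true 80% is recorded as 73%, 50% and 22%. With onset SD 1.2 and entry over weeks 5–15, 5–20 or 5–30, a true 70% is recorded as about 56%, 42% and 25%, with first recorded nausea at weeks 9.5 to 10.5.

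**5. Does the direction hold for every measure?** No.

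- Prevalence at week 10 among women enrolled by week 10 is 59% against a true 59%. If entry is unrelated to nausea, those women are a random sample.
- Suppose only tracker users are counted, and 80% of women with nausea after entry use it against 30% of the rest. Entry over weeks 4–12 then gives 0.639 × 0.8 / (0.639 × 0.8 + 0.361 × 0.3) = 0.511/0.619 = 82.5%, which overstates the true 70%. Weeks 4–20 give 67%, and weeks 4–40 give 39%.

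**6. Would restricting to women enrolled before onset cure the dating?** No. The chance of enrolling before onset grows with (onset − 4), so later onsets are over-represented. Ignoring truncation, the mean becomes 6 + 1.5²/(6 − 4) = 7.1; the simulation gives 7.0 against 6.0.

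**The case against.** The strongest objection is that the questionnaire is not shown and the list in 4.4.2 is not complete. Section 4.4.2.1 places a sleep item in the initial questionnaire that 4.4.2 does not list. Section 4.1 says in general terms that registry questions reach back before conception. The one monthly example in 4.4.2.2, on whether fetal movement has been felt yet, is itself a so-far-in-pregnancy question. Nothing bars a back-dated tracker entry. No section defines onset as the first tracker entry, and denominators are properly left to analysis.

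Most of this stands, and it limits what can be claimed. A reader might infer that the enrolment questionnaire does not ask about earlier nausea. The protocol supports only that no such item is described. A reader might also infer that nausea frequency will be understated whatever the measure. Week-specific prevalence, a natural reading of the 2.3.2 outcome, is not biased by late entry alone, and a tracker-user denominator can reverse the direction.

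It is also fair that nausea is a secondary outcome, offered among examples, in a registry meant to inform later research.

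The objection does not remove the gap. The general coverage statement names no nausea look-back. A date field that neither invites nor forbids past entries is not a plan to collect them. Week-specific prevalence does not answer when nausea begins, or how many women ever have it and for how long.

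**Conclusion.** The point holds in conditional form. Entry is unrestricted by gestational age, nausea frequency, onset and duration are stated questions, and no described item captures nausea earlier in the current pregnancy. Unless one is collected:

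- nausea that ended before joining is missed, and ever-nausea among all enrolees is biased downward;
- onset before joining cannot be dated, and onset read from first tracker entries is biased late.

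The size cannot be derived from the documents. Under the assumed inputs in the table it runs from modest (64% against 70%, about two weeks late) when entry ends by week 12 to severe (20% against 70%, about four weeks late) when entry runs to week 40. These figures assume that women do not back-date entries and that entry is unrelated to nausea. They do not carry over to week-specific prevalence or to analyses of tracker users only. The matter is worth correcting because the loss is permanent and the remedy is cheap.

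**What to change.** In 4.4.2, add to the current-pregnancy items: any nausea or vomiting so far in this pregnancy; the week it began; and, if it has stopped, the week it stopped. If the questionnaire already contains these, list them there and the point is closed.

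Then state how they are used:

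- Report ever-frequency and onset for all enrolees from these items together with later tracker data, by gestational age at entry, showing recalled and prospectively tracked onset separately.
- Report prevalence by gestational week among women enrolled by that week.
- Do not restrict onset to women enrolled before it began unless the analysis allows for delayed entry.

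The cost is two or three questions and a short statement on reporting. Section 4.4.2.4 already expects questions to be added and revised. The downside is recall error, greatest in women who join late, which is why recalled and tracked onset should be kept apart. Adding the items sooner is better, since recall worsens for women already enrolled.
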